3.2 Sample Size

Approximately 100 subjects will be enrolled in the study, with up to 20 subjects to be enrolled in the dose exploration phase (Part 1) and approximately 80 subjects to be enrolled in the dose expansion phase (Part 2).

The sample size in the dose exploration phase (Part 1) is based on practical consideration and is consistent with conventional oncology studies with the objective to estimate the MTD. With 3 subjects in a dose level, there is a 27% to 70% probability of observing at least 1 DLT if the true DLT rate is 10% to 33% and with 4 subjects in a dose level, there

Date: 24 March 2023 Page 16 of 53

is 34% to 80% probability. With 6 subjects in a dose level, there is a 47% to 91% probability of observing at least 1 DLT if the true DLT rate is 10% to 33% and with 10 subjects in a dose level, there is a 65% to 98% probability.

•		
In the dose expansion phase (Part 2), up to	subjects will be enrolled.	Forty subjects
will be enrolled in Part 2		

3.3 Adaptive Design

The guidelines described in protocol Section 4.1 for dose escalation or de-escalation to the next dose level are determined by using a mTPI-2 algorithm (Guo et al, 2017). The mTPI-2 algorithm employs a simple beta-binomial Bayesian model. Let p_T be the target toxicity level and $(p_T - \epsilon 1, p_T + \epsilon 2)$ be the equivalence toxicity interval denoted as EI. The unit toxicity interval (0, 1) is divided into subintervals with equal length given by $(\epsilon 1 + \epsilon 2)$. Let the under-dosing intervals (LI) denote for a set of intervals below EI, and the overdosing intervals (HI) for a set of intervals above EI. The 3 types of dosing intervals (EI, LI, HI) are associated with 3 different dose-escalation decisions. The LI correspond to a dose escalation (E), the HI correspond to a dose de-escalation (D), and proper dosing intervals (EI) correspond to staying at the current dose (S). This study design uses a target toxicity level, p_T of 30%, and EI of (25%,33%). Decision rules are based on the unit probability mass (UPM) calculated on these equal-length intervals. Given an interval and a probability distribution, the UPM of that interval is defined as the probability of the interval divided by the length of the interval. The mTPI-2 design calculates the UPMs for the each of equal-length dosing intervals. If the interval with the largest UPM is from LI, EI or HI, then the corresponding dose decision would be E, S, or D, respectively.

A dose level will be considered unsafe, with no additional subjects enrolled at that dose level, if it has an estimated 95% or more probability of exceeding the target DLT rate p_T (i.e., P [DLT > p_T | data] > 95%). Based on this rule, the following instances would result in a dose level being considered unsafe.

- 3 or more DLTs in ≤ 4 subjects
- 4 or more DLTs in ≤ 6 subjects
- 5 or more DLTs in ≤ 9 subjects
- 6 or more DLTs in 10 subjects

Date: 24 March 2023 Page 17 of 53

After the escalation phase is completed, final DLT rates at each dose level will be estimated by isotonic regression (Ji et al, 2010). The weighted least squares regression model will assume monotonic non-decreasing DLT rates with increasing dose and use the empirical (observed) DLT rates at each dose level as responses and dose level sample sizes as weights, along with the pool adjacent violators algorithm (PAVA) to estimate the DLT rate at each dose level. Given the DLT estimates for each dose level, the MTD will be selected from all tried dose levels that have not been previously declared to be unsafe with a decision according to the mTPI decision table. With this constraint, the MTD will be determined as the dose level with the DLT estimate closest to the target toxicity level of 30%.

4. Covariates and Subgroups

4.1 Planned Covariates

The relationship between relevant covariates and efficacy endpoints may be explored if appropriate. The following baseline covariates may be summarized as appropriate for each study part:

- Race
- Ethnicity
- Sex
- Age at enrollment in years
- ECOG performance status at baseline
- Prior lines of therapy
- Metastatic
- Sum of diameters of target lesions at baseline based on investigator assessment (mm)
- •

4.2 Subgroups

Date: 24 March 2023 Page 18 of 53

5. Definitions

5.1 General Definitions

Baseline

For any variable, unless otherwise specified, the baseline is the last non-missing assessment taken prior to the first administration of tarlatamab. Where baseline measurements are taken on the same day as the tarlatamab administered and no times are present, it will be assumed that these measurements are taken prior to the study specified treatment being administered.

Body Mass Index (BMI)

BMI is calculated using the following formula:

BMI (kg/m^2) = weight (kg) / $[height (cm) / 100]^2$

Change from Baseline

Change from **b**aseline is calculated using the following formula:

[figure not shown]
Change from **b**aseline = **p**ost-baseline **v**alue – **b**aseline **v**alue

End of Investigational Product (IP)

End of IP for each subject is defined as the date the decision was made to end IP as recorded on the End of Investigational Product Administration CRF page.

End of Study (End of Trial)

The end of study date is defined as the date when the last subject across all sites is assessed or receives an intervention for evaluation in the study (i.e., last subject last visit); following any additional parts in the study (e.g., long-term follow-up,

End of Study (Individual Subject)

End of study for each subject is defined as the date the subject last completed a protocolspecified procedure. The date will be recorded on the End of Study CRF page.

End of Study (Primary Completion)

The primary completion is defined as the date when the last subject is assessed or receives an intervention for the final collection of data for the primary endpoint(s).

If the study concludes prior to the primary completion date originally planned in the protocol (i.e., early termination of the study), then the primary completion will be the date

Date: 24 March 2023 Page 19 of 53

when the last subject is assessed or receives an intervention for evaluation in the study (i.e., last subject last visit).

Investigational Product (IP)

Investigational product refers to tarlatamab.

Long Term Follow-up (LTFU)

LTFU will be conducted every 3 months up to 3 years from the last dose of tarlatamab for all subjects who have not withdrawn consent by clinic visit, telephone or chart review to assess for survival and/or the commencement of subsequent cancer therapy only.

For subjects who discontinued treatment for any reason other than progressive disease, every effort should be made to perform radiographic imaging (CT/MRI/bone scintigraphy) of the chest, abdomen, pelvis, bone, and all other known sites of disease every 3 months until documentation of disease progression per PCWG3 guidelines, clinical progression, start of new anticancer therapy, or up to 3 years after the last dose of tarlatamab, whichever occurs first.

Treatment-related serious adverse events and fatal serious adverse events regardless of the cause should be collected during long-term follow-up.

Percent Change from Baseline

Percent change from baseline is calculated using the following formula:

Percent change from baseline = [(post-baseline value - baseline value) / baseline

value] x 100

Relative Dose Intensity

Relative dose intensity is calculated using the following formula:

Relative dose intensity (%) = (Actual cumulative dose / Planned cumulative dose) x 100; where actual cumulative dose = sum of received doses, planned cumulative dose = planned dose accumulated over the actual treatment duration, i.e., 100 mg x (number of records in exposure dataset - 1) + 1 mg. Actual and planned cumulative dose up to the study visit are considered.

Safety Follow-up (SFU)

Upon permanent discontinuation from the study treatment for any reason to further assess the risk of delayed adverse events, a SFU visit will be performed approximately 42 (+ 5) days after the end of the last dose of tarlatamab.

Date: 24 March 2023 Page 20 of 53

Study Day

If the date is after the date of study day 1, then study day is calculated as following:

Study day = (date - date of study day 1) + 1

If the date is before the date of study day 1, then study day is calculated as following:

Study day = (date – date of **s**tudy **d**ay 1)

Study Day 1

Study Day 1 is defined as the date of the first dose of tarlatamab administration to the subject.

Treatment Duration

Treatment duration is calculated using the following formula:

Treatment duration (weeks) = (last dose **date** – first dose **date** + 1) / 7.

5.2 Primary Endpoint-related Definitions

Dose-Limiting Toxicity (DLT)

DLT is defined as any qualifying toxicity that is at least possibly related to tarlatamab with an onset within the first 28 days following first dose with either of the following criteria:

- Grade 3 adverse event lasting more than 3 days (with the exception of fatigue and grade 3 non-febrile neutropenia that improves to ≤ grade 1 within 3 weeks including the use of growth factor support per neutropenia management guidelines [protocol Section 6.8.6]);
- ≥ Grade 4 adverse event regardless of duration (with the exception of grade 4 non-febrile neutropenia lasting less than or equal to 7 days including the use of growth factor support per neutropenia management guidelines [protocol Section 6.8.6]).
- Grade 5 adverse event

Laboratory parameters of Grade 3 or 4 of any duration, not considered clinically relevant, will not be considered DLTs.

Grade 4 electrolyte abnormalities that last < 72 hours, are not clinically complicated, and resolve spontaneously or respond to conventional medical interventions will not be considered DLTs.

Date: 24 March 2023 Page 21 of 53

The following adverse events will NOT be adjudicated as DLT regardless of the grade or duration:

- Lymphopenia
- Fever
- Tumor lysis syndrome (TLS) including associated manifestations attributable to TLS (e.g., electrolyte abnormalities, renal dysfunction, hyperuricemia)

DLT Evaluable

The DLT endpoint is evaluable if either: 1) the subject experiences a DLT, or 2) the subject does not experience a DLT and receives IP as planned in cycle 1 and has been followed for safety events a minimum of 28 days from start of treatment.

Maximum Tolerated Dose (MTD)

The MTD will be selected from all tried dose levels that have not been previously declared to be unsafe with a decision according to the mTPI decision table. The MTD will be estimated using isotonic regression (Ji et al, 2010) and the MTD will be the dose level with the estimated DLT rate closest to 0.30.

Treatment-Emergent Adverse Event (TEAE)

TEAE is defined as adverse events starting on or after first dose of tarlatamab as determined by "Did event start before first dose of investigational product" equal to "No" or missing on the Events CRF, and up to and including 47 days after the last dose of tarlatamab excluding the events reported after End of Study date.

Treatment-related Adverse Event (TRAE)

TRAE is defined as treatment-emergent AE that per investigator review has a reasonable possibility of being caused by **tarlatamab** as indicated on the Events CRF page.

5.3 Secondary Endpoint-related Definitions

Best Overall Response (BOR) per RECIST 1.1

The subject's best response assignment will depend on the findings of both target and non-target disease and will also take into consideration the appearance of new lesions and confirmation of response. Confirmation of progressive disease is not required. Best overall response (BOR) will be based on all post-baseline disease assessments that occur prior to the initiation of subsequent anticancer treatment. At least 7 weeks from the first dose of IP must elapse without radiological disease progression to meet the minimum criteria for SD duration in order to assign a best overall response of SD. In general, subjects not classifiable under the RECIST 1.1

Date: 24 March 2023 Page 22 of 53

response categories due to inadequate data or early death will be classified as non-evaluable (NE) for BOR but will be counted in the denominator of all response rate calculations. The BOR will depend on the findings from MRI/CT scans. BOR per RECIST 1.1 has the following possible categories: complete response (CR), partial response (PR), stable disease (SD), progressive disease (PD) or not evaluable (NE). The rules for deriving the BOR are detailed in Appendix D.

Disease control rate (DCR)

DCR is defined as the **proportion** of subjects with a best overall response of confirmed response (CR/PR) or SD as per RECIST 1.1.

Duration of Response (DOR) per RECIST 1.1

DOR is defined as the time from the date of an initial objective response per RECIST 1.1 to the earlier of progressive disease per RECIST 1.1 or death for subjects with an objective response. **DOR** will be censored following the same censoring strategy as radiographic progression-free survival as detailed in Appendix B.

Objective Response (OR) per RECIST 1.1

OR is defined as best overall response of PR or CR per RECIST 1.1, confirmed by an assessment at least 4 weeks later. Subjects who do not experience a PR/CR or do not have any follow-up tumor assessments will be regarded as non-responders.

Objective Response Rate (ORR)

ORR is defined as the **proportion** of subjects with a best overall response of **confirmed** CR or PR per RECIST 1.1.

Overall Survival (OS)

OS is defined as the time from the start of treatment until event of death due to any cause. Subjects still alive will be censored at the date last known to be alive. If the date last known to be alive is after the date that triggers the analysis (i.e., the data cut-off date), the subject will be censored at the data cut-off date.

Radiographic Progression:

A radiographic progression occurs if either of the following occurs:

- Progressive disease in soft tissue per RECIST 1.1.
- Bone disease progression as per PCWG3. Bone disease progression for the first post-treatment bone scan (e.g. week 8) showing two or more additional lesions relative to screening/baseline must be confirmed by the next bone

Date: 24 March 2023 Page 23 of 53

scan (e.g. week 16) showing two or more additional lesions relative to the first post-treatment bone scan (e.g. week 8). Bone disease progression for scans after the first post-treatment scan (e.g. week 16) showing two or more additional lesions relative to first post-treatment bone scan (e.g. week 8) must be confirmed by a later scan showing two or more additional lesions relative to the first post- treatment scan (e.g. week 8).

[figure not shown]
Rules to derive timepoint radiographic progression by RECIST 1.1 with PCWG3 modifications are detailed in Table 14-6.

Radiographic Progression-free Survival (rPFS)

rPFS is defined as the interval from the first dose of tarlatamab to the earlier of a radiographic progression or death from any cause. **Censoring is at the last evaluable disease assessment date (tumor assessment or bone scan) based on the** rules detailed in Appendix B.

[figure not shown]
PFS = (PD or death date - start of treatment date + 1) \times 12 / 365.25

5.4 Exploratory Endpoint-related Definitions

Date: 24 March 2023 Page 24 of 53

6. Analysis Sets

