Abbreviations used: Ab = antibody; ACTH = adrenocorticotropic hormone; AE = adverse event; BP = blood pressure; C = cycle; CBC = complete blood count; [REDACTED] CNS = central nervous system; COVID-19 = Coronavirus Disease 2019; CRP = C-reactive protein; CRS = Cytokine Release Syndrome; [REDACTED] D = day; ECG = electrocardiogram; ECHO = echocardiogram; ECOG = Eastern Cooperative Oncology Group; eCRF = electronic case report form; EOI = end of infusion; EOT = end of treatment; [REDACTED] FSH = follicle stimulating hormone; FT4 = free thyroxine; HBsAg = hepatitis B surface antigen; HBsAb = anti-hepatitis B surface antibody; HCV = hepatitis C; HIV = human immunodeficiency virus; HR = heart rate; IHC = immunohistochemistry; IGF-1 = insulin-like growth factor 1; IP = investigational product; IPIM = Investigational Product Instruction Manual; IV = intravenous; [REDACTED] LH = luteinizing hormone; LTFU = long-term follow-up; MMSE = Mini Mental Status Examination; MRI = magnetic resonance imaging; MUGA = multigated acquisition; NE = neuroendocrine; [REDACTED] PCWG3 = Prostate Cancer Working Group 3; PD = progressive disease; PK = pharmacokinetic; Pre = pre-infusion; [REDACTED] PTEN = phosphatase and tensin homolog; Q cyc = every cycle; Q2 Cyc = every 2 cycles; Q3 Cyc = every 3 cycles; RB1 = retinoblastoma protein; RECIST = Response Evaluation Criteria in Solid Tumors; RR = respiratory rate; SAE = serious adverse event; SCR = screening; SFU = safety follow-up; SOA = Schedule of Activities; SOI = start of infusion; TLS = tumor lysis syndrome; Tp53 = tumor protein p53; TSH = thyroid stimulating hormone

- a All screening procedures should be performed within 28 days prior to cycle 1 day 1 dosing.
- b Each visit week and day is relative to day 1 of each cycle. Cycle 1 and cycle 2 visits have a \pm 1-day window from designated time point unless otherwise specified. All subsequent visits beginning in cycle 3 will have a \pm 3-day window.
- c
 - End of infusion (EOI) assessments or procedures are to be completed immediately after infusion of tarlatamab. EOI indicates the time when the IP infusion and saline flush is completed. Assessments after EOI indicate the time relative to EOI. Investigational product infusions are marked in the EOI column.
 - Assessments are done pre-infusion unless specified.

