4.1 Overall Design

This is an open label phase 1b study evaluating tarlatamab monotherapy.

[figure not shown]
Tarlatamab will be administered as a short-term IV infusion Q2W (with step dosing) in a 28-day cycle as monotherapy therapy in subjects with de novo or treatment-emergent NEPC.

The study will consist of 2 parts: dose exploration (Part 1) and dose expansion (Part 2).

Dose Exploration (Part 1)

The dose exploration part of the study will enroll up to 20 subjects with relapsed/refractory (RR) NEPC. At the time of initiation of the study, the starting dose will be the highest dose deemed safe and tolerable in the ongoing phase 1 trial of tarlatamab in subjects with small cell lung cancer (Note: based on emerging safety data

from Study 20160323, the starting dose may be lower than the highest dose deemed safe and tolerable). The planned highest dose in this study is not anticipated to exceed the maximum tolerated dose (MTD) as established in the ongoing Study 20160323. Based on results from study 20160323 in small cell lung cancer, the doses that may be explored in this study are presented in [Table 4-1](#).

Due to its known mechanism of action, subjects are at an increased risk for first dose effects (eg, CRS with associated manifestations and any other potentially evolving and unknown first dose effects) following the initial infusion of tarlatamab. To mitigate these risks, a step dosing approach will be implemented. One of the following step dosing approaches will be utilized as the initial dosing schedule based on emerging data and the dosing schedule associated with the highest dose deemed safe and tolerable from the ongoing first-in-human (FIH) study (Note: based on emerging safety data from Study 20160323, the starting dose may be lower than the highest dose deemed safe and tolerable).

- Single-step dosing involving a run-in dose on day 1, followed by a step dose on day 8 (equal to the target dose) and the target dose on day 15 then Q2W.

Based on emerging safety, pharmacokinetic and pharmacodynamic data from this study as well as the ongoing FIH study (20160323) and the recommendations of the DLRT, multiple or parallel dosing cohorts may also be opened simultaneously to assess any of the step-dosing strategies as described above.

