Due to its known mechanism of action, subjects are at an increased risk for first dose effects (eg, cytokine release syndrome) following the initial infusion of tarlatamab. To mitigate these risks, a step dosing approach will be implemented (involving a run-in dose on cycle 1 day 1 followed by one [REDACTED] step doses) per the recommendations of the DLRT and based on emerging data from the ongoing phase 1 trial in small cell lung cancer.

Dose Expansion (Part 2)

Once the recommended phase 2 dose (RP2D) has been determined, enrollment will commence in the dose expansion phase to confirm the safety and tolerability of the selected dose and to further evaluate anti-tumor activity.

One or more dosing schedules as described in Part 1 may be pursued in parallel during the expansion phase.

Interim futility analyses (non-binding) will be performed in a continuous manner using Bayesian predictive probability (Lee & Liu, 2008). Interim futility analyses will begin after approximately 20 subjects have been treated and have met the data cutoff criteria defined as a minimum potential follow-up of 9 weeks. Following this initial interim futility analysis subsequent interim futility analyses will be performed after every 10 subjects

have reached the data cutoff criteria, until all subjects are enrolled and evaluated. Further enrollment may be terminated if futility criteria are met in the interim futility analysis.

The interim safety analyses will begin after n=10 dose expansion subjects have had the opportunity to be on treatment for at least 28 days. Following this initial interim safety analysis, subsequent interim safety analyses will be done together with interim futility analyses i.e. after every 10 dose expansion subjects have a minimum potential follow-up of 9 weeks. Based on the interim safety results and reviewing an update estimate of the MTD or RP2D using all available data including data from dose exploration and expansion subjects, the DLRT may modify the dose level of treated subjects. A final estimate of the MTD or RP2D will use all data from dose exploration and dose expansion.

Based on emerging data from the tarlatamab monotherapy in this indication and emerging data from other trials with tarlatamab, the protocol may be amended to include a combination of tarlatamab with anti-PD-1 (L1) agent.

The overall study design is described by a study schema in Section 1.2. The endpoints are defined in Section 3.

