6.1 Treatment(s) Administered

6.1.1 Investigational Products

Table 6-1. Study Treatments

Amgen Investigational Product:^a	
Study Treatment Name	Tarlatamab
Dosage Formulation	Tarlatamab is supplied as a sterile, single use, preservative free lyophilized drug product containing [REDACTED] mg of tarlatamab per vial. Tarlatamab is intended for reconstitution with sterile water for injection and dilution in an IV bag with normal saline ([REDACTED] sodium chloride) and an IV solution stabilizer. The drug product is formulated with L-glutamic acid, sucrose, polysorbate 80, pH [REDACTED]
Unit Dose Strength(s)/ Dosage Level(s) and Dosage Frequency	At the time of initiation of the study, the starting dose will be the highest dose deemed safe and tolerable in the ongoing phase 1 trial of tarlatamab in subjects with small cell lung cancer (Note: based on emerging safety data from Study 20160323, the starting dose may be lower than the highest dose deemed safe and tolerable).
Route of Administration	Tarlatamab will be administered as a short-term IV infusion for 60 minutes followed by a flush once every 2 weeks (with step-dosing).
Accountability	The date, time, package lot number, dose, and the start and stop time of infusion are to be recorded on the individual subject's Investigational Product Administration CRF.
Dosing Instructions	Tarlatamab will be administered at the study center by a qualified staff member. A physician must be available at the time of administration of investigational products. Please refer to IPIM for more details on dosage, administration, and schedule of tarlatamab.

CRF = case report form; IPIM = Investigational Product Instruction Manual; IV = intravenous.

^a Tarlatamab will be manufactured and packaged by Amgen Inc. and distributed using Amgen clinical study drug distribution procedures.

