6.2.2.1.2 Dose Delays

During the first 28 days DLT observation period, if the dosing of tarlatamab is delayed for more than 72 hours for reasons other than DLT during the DLT evaluation period, a replacement subject may be enrolled and assigned to the same dose level. The subject may continue on study only after discussion with the Medical Monitor.

After the 28-day DLT observation period, if the dosing of tarlatamab is delayed for ≤ 2 weeks, the subject should resume the treatment as soon as possible if deemed safe by the investigator. The investigator should inform the Amgen Clinical team as soon as the unexpected dosing interruption occurs. If the dosing of tarlatamab is delayed between 2 to 4 weeks due to severe or life-threatening treatment-related adverse events, the subject can resume treatment if the toxicities resolve to grade ≤ 1 or return to subjects' baseline values within 4 weeks and restarting of therapy has been deemed safe by the investigator and medical monitor.

If the dosing of tarlatamab is delayed for more than 4 weeks due to severe or life-threatening treatment-related adverse events, the subject will be discontinued from investigational product (IP). If the dosing delay occurred under other conditions, the

case will be reviewed by the Sponsor to determine whether and when the subject will be allowed to resume tarlatamab.

For adverse events related to CRS, neurological events, and pituitary dysfunction, please see Sections 6.8.1, 6.8.2, and 6.8.3 respectively for guidelines for dose delays.

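### SAP 5.1 equates planned dose over the treatment duration with a count of exposure records, so a late or unrecorded dose can leave relative dose intensity at 100%

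*SAP*

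**What the plan says.** SAP 5.1 sets RDI as actual over planned cumulative dose, times 100. Actual dose is the sum of doses received. Planned dose is "planned dose accumulated over the actual treatment duration, i.e., 100 mg x (number of records in exposure dataset - 1) + 1 mg". The next sentence adds: "Actual and planned cumulative dose up to the study visit are considered". Further down the same section, "Treatment duration is calculated using the following formula" introduces last dose date minus first dose date plus 1, divided by 7.

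Protocol 4.1 opens single-step dosing with a run-in dose on the first day. The rest of the schedule reads: "followed by a step dose on day 8 (equal to the target dose) and the target dose on day 15 then Q2W". Protocol 6.2.2.1.2 foresees delays of up to 2 weeks and, separately, longer ones ("If the dosing of tarlatamab is delayed between 2 to 4 weeks"), with treatment resumed under conditions. On data capture, Protocol Table 6-1 says: "The date, time, package lot number, dose, and the start and stop time of infusion are to be recorded on the individual" subject's administration CRF.

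SAP 9.6.8 lists four exposure summaries: number of doses, cumulative dose, RDI and treatment duration.

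**The concern.** RDI is meant to show how much of the scheduled treatment was delivered over the time the subject was treated. The SAP's words say that; its formula counts rows. The two agree only if the exposure dataset holds one row per scheduled visit, including visits where nothing was given. Neither document defines a record in that dataset, and the CRF description in Table 6-1 concerns infusions that took place. The sentence about the study visit does not settle the matter, because it truncates actual and planned dose alike and adds nothing for elapsed time.

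At stake is whether the exposure table shows delays and omissions. Of the four summaries in SAP 9.6.8, RDI is the only one that sets delivery against plan. The separate summary of dose modifications in Protocol 9.4.2.3.8 is not listed there.

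**Working it through.** The documents give no numerical RDI, so there is no figure to reproduce. The check applies both halves of the definition to the same dosing histories.

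**Inputs**
- Doses of 1 mg then 100 mg: the constants in the SAP formula.
- Scheduled days 1, 8, 15, 29, 43, 57, 71, 85, then every 14 days: Protocol 4.1.
- Delays of 2 and 4 weeks: the upper ends of the two categories in Protocol 6.2.2.1.2. The delay is placed before dose 5, and later doses move by the same amount.
- Assumed: the numbers of doses and delay patterns, and a planned schedule anchored to the first dose.

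**Formulas**
- By the formula: planned = 100 × (n − 1) + 1, where n is the number of records, one per dose given.
- By the wording: planned = 100 × (k − 1) + 1, where k is the number of scheduled doses on or before the last dose date.

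| History | Last dose (duration) | Actual mg | By the wording | By the formula |
|---|---|---|---|---|
| 8 doses on time | day 85 (12.14 wk) | 701 | k = 8: 701/701 = 100% | n = 8: 701/701 = 100% |
| One 1-week delay | day 92 (13.14 wk) | 701 | k = 8: 701/701 = 100% | n = 8: 100% |
| One 2-week delay | day 99 (14.14 wk) | 701 | k = 9: 701/801 = 87.5% | n = 8: 100% |
| One 4-week delay | day 113 (16.14 wk) | 701 | k = 10: 701/901 = 77.8% | n = 8: 100% |
| Two 100 mg doses of 8 omitted, last dose still day 85 | day 85 (12.14 wk) | 501 | k = 8: 501/701 = 71.5% | n = 6: 501/501 = 100% |

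**Longer exposure.** The gap shrinks. With one 2-week or 4-week delay, the wording gives:
- 13 doses: 1201/1301 = 92.3% or 1201/1401 = 85.7%.
- 26 doses: 2501/2601 = 96.2% or 2501/2701 = 92.6%.

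The formula with one record per dose gives 100% throughout.

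**With zero-mg rows.** If each missed scheduled slot leaves a row, the formula gives 701/801 = 87.5% (n = 9), 701/901 = 77.8% (n = 10) and, for the omissions, 501/701 = 71.5% (n = 8). Words and formula then agree. The convention still has to be exact: a zero-mg row logged for the 1-week delay would give 701/801 = 87.5% by the formula against 100% by the wording.

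**Dose reductions.** These are captured. If the last two of 8 doses are given at d mg, RDI is (501 + 2d)/701, which is below 100% for every d under 100.

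**The case against.** The strongest reply is that the planned schedule may move with a delay. Protocol 1.3 footnote b places visits relative to day 1 of each cycle, Protocol 8.2.2.1 keeps imaging on time irrespective of dose delays, and Protocol 6.2.2.1.2 has a subject delayed up to 2 weeks resume as soon as possible. If later visits shift, a delay with all doses given skips no planned visit, and a record count is right. This much stands: the 87.5% and 77.8% depend on anchoring the schedule to the first dose, which the SAP does not state. It does not remove the contradiction, because on that reading the reference to actual treatment duration would do no work for delays. Nor does it help with an omission where the remaining doses stay on their days.

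Second, the dataset may hold zero-mg rows. It may, and the two halves would then agree. The result would still rest on a convention that neither document gives.

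Third, RDI is only descriptive. That is correct. Number of doses, cumulative dose, treatment duration and adverse events leading to interruption (SAP 9.6.2) are also reported, so delays can be inferred indirectly.

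A reader might also infer that the fixed 1 mg and 100 mg misstate RDI for subjects on other doses. The protocol does say that "the DLRT may modify the dose level of treated subjects", but the dose levels are redacted, the constants fit single-step dosing, and nothing visible shows a subject assigned another regimen. This is a reason to write the repair in terms of assigned dose, not a demonstrated error.

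**Conclusion.** The definition contradicts itself: it describes a duration-based quantity and then replaces it with a row count that has no time or schedule term. With one record per dose given and none for omissions, RDI stays at 100% after delays and omissions. In the eight-dose illustration the wording gives 87.5%, 77.8% or 71.5%. These figures assume the 1 mg then 100 mg regimen and invented dosing histories; the two delay figures also assume a schedule fixed to the first dose.

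Severity is minor. A reader might infer that this trial's RDI will read 100% whatever happens, or that its safety conclusions are compromised. The documents support neither: the record convention is not visible, dose reductions do lower RDI, and no endpoint, stopping rule or dosing decision uses it.

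**What to change.** Replace the record-count formula in SAP 5.1. Define planned cumulative dose as the sum of the subject's own assigned doses scheduled from first to last dose date, whether or not each was given. State that the schedule is anchored to the first dose date and does not shift after a delay. RDI remains actual over planned, times 100.

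Three rules belong with it:
- **Early final dose.** Count a final dose given early but within the visit window as scheduled. Protocol 1.3 footnote b says: "All subsequent visits beginning in cycle 3 will have a" window of plus or minus 3 days. Without this rule, an 8th dose on day 82 instead of day 85 would have 7 scheduled doses and 701/601 = 116.6%; with it, 701/701 = 100%.
- **Omitted and withheld doses.** State that they stay in the denominator at the assigned amount.
- **Re-assigned doses.** State from when a changed assignment enters the plan, so that a dose reduction still lowers RDI.

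The cost is one SAP definition and one derivation, from dose dates and amounts the protocol already has recorded. Reported RDI may be lower. Counting whole scheduled doses is also coarse: in the illustration a 1-week delay costs nothing and a 2-week delay costs a full dose. Lateness within the window can add up too. If windows run from each cycle's actual day 1, five cycles each 3 days late make 15 days, enough to add one scheduled dose. The SAP should say that this is intended.
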